#### 2.11 Unscheduled Visits

An unscheduled visit may be performed at any time during the study at the subject's request or as deemed necessary by the site Investigator. The date and reason for the unscheduled visit will be recorded in the source documentation.

#### 2.12 Replacement of Subjects

Replacement of subjects who have withdrawn or been withdrawn from the study will be allowed to be replaced with prior approval from the sponsor and/or IRB.

# CUNO(URE

## **2.13 Schedule of Visits and Procedures**

	Visit #1	Visit #2-6	Call #1 or Visit (optional)	Call #2 or Visit #7	Visit #8	Visit #9 (optional)
Procedure	Screening and Pretreatment Procedures*	Treatment Visit(s) 1-5 Every 4 Weeks (+/- 2 weeks)	Phone Call 24 Hours Post Each Tx	Phone Call or Visit 1 Week Post Each Tx (2-10 Days)	Follow Up 30 Days Post Last Tx (+/- 1 Week)	Follow Up 90 Days Post Last Tx (+/- 2 Weeks)
Medical History	Х					
Pregnancy Verification	Х	X**				
Informed Consent	Х					
Photographs	Х	Х	Х	Х	Х	Х
Treatment		Х				
Treatment Discomfort/ Pain Evaluation		Х				
Subject Questionnaires		Х		Х	Х	Х
Clinician Questionnaires		Х		Х	Х	Х
Adverse Events Assessment		Х	Х	Х	Х	Х

\*Screening and Pretreatment Procedures may occur at the same time as the first Treatment Visit. Must be performed at least 30 days prior to first treatment.

\*\*Pregnancy verification will only be required to be performed prior to each treatment if the treatment is on the abdomen.

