## 2.0 PROTOCOL

## 2.1 Protocol Methodology and Analysis

## Methodology:

Subjects are to be enrolled in this clinical study if they are 18 - 55 years old. Up to 120 subjects will be enrolled at 5 study centers. Subjects may receive up to 5 treatments with the PotenzaTM device if they present with conditions such as, but not limited to; Wrinkles, fine lines, crepey skin, acne scars, active acne, enlarged pores, stretch marks, or loose skin on the face, neck and/or body.

Subjects will attend a screening/pretreatment visit which may be performed on the same day as the treatment visit. Subjects will receive up to 5 treatments. All subjects may receive a phone call or attend a visit 24 hours post each treatment and will receive a phone call or attend a visit 1 week (2-10 days) after each treatment to record side effects. Subjects will be required to return for a follow-up visit 30 days after the final treatment. Subjects may also attend an optional follow up visit 90 days after the final treatment. An unscheduled visit or phone call may be performed at any time during the study at the request of the subject or as deemed necessary by the site Investigator.

Analysis:

Upcoming generations are proving to have an interest in aesthetic dermatology treatments and will drive demand for innovated products, procedures, and practice design. Due to this shift in patient base, practices need to evolve to adapt to the newer generational ideologies. There have been rapid advances in RF technology over the past few years and the nonsurgical treatment using this energy source offers great promise to our aging population. Radiofrequency micro needling technology for the treatment of dermatologic conditions needs to be further investigated to optimize treatment parameters for safe and effective non-ablative treatments.

Relevance: Does not apply to this study – feasibility study.

Testability: Does not apply to this study – feasibility study.

Compatibility: Does not apply to this study – feasibility study.

Predictive power: Does not apply to this study – feasibility study.

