#### 2.6 Pre-Treatment Procedures

If the subject is of childbearing potential (i.e. females not post-menopausal or not surgically sterile), then they will be asked if they are pregnant, the date of their last menstrual cycle, and perform a pregnancy test. If the treatment is on the abdomen, a urine pregnancy test must be performed before each treatment. A urine pregnancy test may be conducted at the Investigators discretion during the study. If a urine pregnancy test is conducted, then a negative result must be obtained within 24 hours prior to the treatment.

Urine Pregnancy Test Procedure:

- 1. A urine sample is tested mid-stream or by cup sample with an indicator stick.
- 2. Negative results are indicated on the indicator stick.
- The following Pre-Treatment instructions will be reviewed:
  - Remove all jewelry and makeup, including eye makeup, lotions or sun block and wash facial area prior to treatment.
  - For an optimum treatment, keep hydrated by drinking water (at least 8 cups daily) or hydrating fluids, such as Gatorade, and avoid drinking alcohol for several days in advance.
  - For five to seven days prior to treatment, at the physician's discretion, avoid therapies that may cause erythema (redness) or irritation such as Retin A or products containing Isotretinoin, glycolic and or salicylic acid.
  - Shave visible hair from the treatment area. Male beards should be shaved day of treatment. RF follows the path of least resistance and the hair will receive the energy.
- Photographs will be taken prior to the first treatment.

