## 11.0 PREGNANCY

Females may not participate in this study if they are pregnant, breastfeeding, were pregnant within the last three months or are planning a pregnancy during the study.

If the subject thinks they have become pregnant during the study, it is important that they inform the Investigator immediately. If she becomes pregnant or thinks that she may be pregnant, she will be removed from the study and will be asked to perform a final evaluation similar to that of the final follow-up visit. The Investigator may request to track the pregnancy and will report the pregnancy to the Sponsor.

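### The screening footnote in section 2.13 cancels the same-day option it grants, and the schedule omits the pre-treatment pregnancy test that section 2.6 requires

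*Combined protocol and SAP*

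**What the plan says.** **Timing of screening.** The single-asterisk footnote in section 2.13 says that screening and pretreatment work "may occur at the same time as the first Treatment Visit. Must be performed at least 30 days prior to first treatment". The first sentence is a permission. The second, with no condition attached, sets a minimum lead of 30 days. Section 2.1 agrees with the permission: "Subjects will attend a screening/pretreatment visit which may be performed on the same day as the treatment visit". It gives no minimum interval, and no other section does.

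**Pregnancy testing in the text.** Section 2.6 says of subjects of childbearing potential: "then they will be asked if they are pregnant, the date of their last menstrual cycle, and perform a pregnancy test". It adds a limit on the age of the result: "If a urine pregnancy test is conducted, then a negative result must be obtained within 24 hours prior to the treatment". For one body area it goes further: "If the treatment is on the abdomen, a urine pregnancy test must be performed before each treatment". It also lets the investigator order a urine test at any point in the study.

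**Pregnancy testing in the schedule.** The pregnancy row in 2.13 is marked at Visit 1 and, with a double asterisk, at the treatment visits. The double-asterisk footnote reads: "Pregnancy verification will only be required to be performed prior to each treatment if the treatment is on the abdomen".

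**Other protections.** Section 2.3 excludes pregnant subjects and those of childbearing potential who are not using effective birth control. Section 11.0 asks for self-report: "If the subject thinks they have become pregnant during the study, it is important that they inform the Investigator immediately".

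**The concern.** A permission and an unconditional requirement stand side by side in the table that sites work from, and the requirement removes what the permission gives. A coordinator who screens and treats on one day follows section 2.1 and the first sentence but breaches the second. Section 21.0 permits no deviation without sponsor approval outside a medical emergency, and sections 15.0 and 18.0 require deviations to be reported. Which sentence is applied therefore decides whether routine same-day screening counts as a deviation. It could also affect membership of the optional per-protocol set in 2.16.3, which depends on completing the trial as the protocol specifies.

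The second consequence concerns safety. Visit 1 pregnancy verification sits in the column that the footnote governs. If Visit 1 is moved 30 days or more ahead, its test is too old under section 2.6, and the schedule prompts no replacement before a first treatment to the face, neck or any other area off the abdomen. Pregnancy is an exclusion, so the schedule ought to carry this check.

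**Working it through.** The point involves no sample size, power or error rate, and the plan states no figure to reproduce. The check compares the rules and adds some date arithmetic.

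**1. Permitted lead from screening to first treatment**

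| Source | Lead allowed |
|---|---|
| 2.13, footnote *, first sentence | 0 days allowed |
| 2.13, footnote *, second sentence | 30 days or more required |
| 2.1 | 0 days allowed, no minimum |

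A lead of 0 days fits rows 1 and 3 and fails row 2. A lead of 30 days or more breaches none of them, because rows 1 and 3 only permit. What the second sentence removes is the same-day option.

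**2. Age of the Visit 1 pregnancy test at first treatment**

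Inputs: the 30-day minimum (2.13) and the 24-hour limit for a urine test (2.6).

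- Under the 30-day sentence: age ≥ 30 × 24 = 720 hours, which exceeds the limit by at least 720 − 24 = 696 hours.
- Under same-day screening: the Visit 1 test can meet the limit.
- If the sentence were reworded as a 30-day maximum: age from 0 to 720 hours, and any lead over 24 hours still fails.

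**3. Scheduled tests that can meet the 24-hour limit at first treatment**

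| Treatment area | Same-day screening | Lead over 24 hours |
|---|---|---|
| Abdomen | At least 1 | 1 (double-asterisk test at the treatment visit) |
| Off the abdomen | 1 (Visit 1 test) | 0 |

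Only the last cell is a gap in the schedule. Section 2.6, read literally, still calls for a fresh negative result there.

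**4. Fit with the stated duration**

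Section 1.3 allows up to 9 months of participation. Inputs: five treatments, hence four intervals, of 4 weeks with a tolerance of 2 weeks (2.7), and an optional last visit at 90 days with a tolerance of 2 weeks (2.13). Months are taken as 30.4 days.

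- Longest course, same-day screening: 4 × 42 + 90 + 14 = 272 days, about 8.9 months.
- With a 30-day lead: 272 + 30 = 302 days, about 9.9 months.
- Nominal spacing: 4 × 28 + 90 = 202 days, or 232 days with the lead. Both fit.

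Consent is taken at Visit 1, so the lead counts toward participation. The 9-month limit sits better with same-day screening, but only at the outer edge of the windows. This is supporting evidence, not proof of intent.

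**The case against.** The strongest reply is that the second sentence is a slip for a maximum of 30 days, that section 2.6 is the operative procedure, and that only a site ignoring 2.6 would reach treatment without a valid test. Much of this stands. A maximum window would agree with section 2.1 and with the duration in 1.3. Section 2.6 does require the test. The birth-control criterion in 2.3 and the discretionary testing in 2.6 also reduce the risk, so self-report under 11.0 is not the only remaining protection, although neither replaces a scheduled test.

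Two things survive. The documents do not state the intended wording, so sites cannot be expected to supply it. And reading the sentence as a maximum does not repair the schedule, because step 2 shows that a test within such a window can still be up to 720 hours old.

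A reader might infer that no site can comply with both footnote sentences. The wording does not support that: the first sentence is permissive, so a site that always screens 30 or more days ahead breaches neither. A reader might also infer that the protocol lets subjects be treated with no pregnancy check. Section 2.6 rules that out.

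**Conclusion.** The conflict is real and should be corrected. The 30-day sentence cancels the same-day screening granted in the same footnote and in section 2.1. Read literally, it makes every same-day-screened subject a deviation. Its wording reaches every subject (up to 120 at 5 centers), but that is the reach of the rule and not a count of deviations, since the documents do not say how many are screened on the day of treatment.

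On pregnancy, the schedule disagrees with section 2.6 in one situation: a subject of childbearing potential, first treated off the abdomen, with screening more than 24 hours earlier. There the schedule provides no test that can meet the limit. The number of such subjects is not given, so none is claimed. The conclusion assumes that the Visit 1 test is a urine test, the only kind whose procedure section 2.6 describes and the only kind to which its 24-hour limit applies.

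The point concerns site compliance and subject safety. It does not alter an endpoint, the primary analysis or any statistical figure.

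**What to change.** Make two edits to section 2.13.

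1. Delete the 30-day sentence from the single-asterisk footnote, or replace it with a maximum window that expressly includes the day of first treatment. The sponsor must choose, because the documents do not show what was meant.
2. Amend the pregnancy row and the double-asterisk footnote to show a negative urine test within 24 hours before the first treatment for all subjects of childbearing potential, whatever the treatment area. This is needed under either choice in edit 1. Testing before treatments 2 to 5 can stay as written.

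The cost is one footnote sentence, one schedule row and its footnote, in an amendment that needs IRB approval under section 21.0. No visits are added. A site that now relies on the schedule alone may perform a urine test it would have omitted, but section 2.6 already calls for that test, so nothing is added to what the protocol requires.

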## CUNO(URE

## **Biopsy Schedule of Visits and Procedures:**

	Biopsy #1	Biopsy #2	Biopsy #3	Biopsy #4	Post Biopsy Visit #1	Biopsy #5	Post Biopsy Visit #2
Procedure	Treatment Visit (control)	0-24 Hours Post Treatment	25-48 Hours Post Treatment	3-7 Days Post Treatment	Follow Up 1 Week Post Biopsy #4 (7-14 Days)	Follow Up 30 Days Post Tx (+/- 1 Week)	Follow Up 1 Week Post Biopsy (7-14 Days)
Biopsy	Х	Х	Х	Х		Х	
Suture Removal					Х		Х
Photographs	Х	Х	Х	Х	Х	Х	Х
Adverse Events Assessment	Х	Х	Х	Х	Х	Х	Х

## 2.14 Evaluation Methods

## **Photographs:**

Photographs will be taken at all visits and will be used to assess safety and efficacy of treatment.

#### **Treatment Discomfort/Pain Evaluation:**

Subjects will be asked to report the general level of treatment discomfort on a scale of 0 (none) to 10 (maximum intolerable pain) using the universal pain assessment tool (Appendix B)

#### **Subject Questionnaire:**

The subject will be asked their level of satisfaction using a 6-point Likert scale that ranges from "extremely satisfied" to "extremely unsatisfied."

Subject Satisfaction			
Rating	Description		
6	Extremely Satisfied		
5	Satisfied		
4	Slightly Satisfied		
3	Slightly Unsatisfied		
2	Dissatisfied		
1	Extremely Unsatisfied		

#### **Physician Questionnaire:**

The Clinical Global Aesthetic Improvement Scale (CGAIS) ranging from "worse" to "very much improved" will be used to judge the improvement as seen by the treating Investigator.

Global Aesthetic Improvement Scale Assessment				
Rating	Description			
1	Very Much Improved- Optimal cosmetic result in this subject			
2	Much Improved- Marked improvement in appearance form the initial			
2	condition, but not completely optimal for this subject.			
2	Improved- Obvious improvement in appearance from initial condition, but a			
3	re-treatment is indicated.			
4	No Change- The appearance is essentially the same as the original condition.			
5	Worse- The appearance is worse than the original condition.			

#### **Blinded Evaluation:**

Three blinded independent reviewers will perform a photographic evaluation in which they will be asked to identify pre-treatment images when compared to post treatment images. The reviewers will be Board Certified Dermatologist and be chosen based on availability and have relevant clinical experience. They will attend a training session prior to grading.

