#### 2.16 Statistical Analysis

#### 2.16.1 Hypothesis

For this study to be considered a success, the Investigator and subject satisfaction rates will be  $\geq 80\%$  and if the side effect profile is acceptable to the Physician as it relates to this type of treatment. In cases where the subject's improvement is being graded on a scale, such as the GAIS scale, we will test the statistical significance of our results against a hypothetical population that would have no change (average score of 4).

For secondary objectives to be considered a success, the results from any assessments will need to be statistically significant or have  $\geq 80\%$  response rate.

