#### 2.16.5 Analysis of Efficacy Variables

The primary efficacy variable is the change from baseline to visit 8 (30 days post last treatment) with respect to the treated condition evaluated by physician grading with CGAIS. Baseline is defined as the last assessment prior to the first treatment. The change from baseline to visit 8 will be analyzed using a Mixed Model Repeated Measures Analysis of Variance. A pairwise treatment group comparison at visit 8 will be performed using the results of this analysis. If a patient has no post-baseline assessment of the primary efficacy variable the patient data will be excluded from the statistical analysis of the improvement. Statistical significance with respect to the treatment group comparison at visit 8 will be declared if the two-sided p-value is < 0.05. For each treatment group summaries will be prepared for both the observed assessment and the change from baseline. Subject satisfaction results from Visit 9 will also be included in the summary. The summaries will include the sample size, mean, median, standard deviation, minimum, and maximum. Categorical variables will also include a summary which will include the number and percent of patients for each outcome. The statistical significance of the mean change from baseline for each treatment group will be determined using a student's paired t-test.

The secondary efficacy variables will be determined at a later date based on image grading. As with the primary efficacy variable the assessment at Visit 8 (30 days post last treatment) will be primary. The analysis and summaries for any secondary efficacy variables will be the same as that described for the primary efficacy variable. Statistical significance with respect to the treatment group comparison at visit 8 will be declared if the two-sided p-value is < 0.05.

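### The three blinded photograph reads have no per-subject result or usable analysis, so the unit of analysis and the combining rule stay open until after the reads

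*Combined protocol and SAP*

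**What the plan says.** Section 2.14 (Blinded Evaluation) says that "Three blinded independent reviewers will perform a photographic evaluation" and that "they will be asked to identify pre-treatment images when compared to post treatment images". It adds the reviewers' qualifications and a training session. It gives no majority, consensus, adjudication or averaging rule. It also does not state outright that every reviewer sees every pair.

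Section 2.16.1 sets the hurdle: "For secondary objectives to be considered a success, the results from any assessments will need to be statistically significant or have" a response rate of at least 80%. It does not say whether a response belongs to a read, a reviewer or a subject.

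Section 2.16.5 says "The secondary efficacy variables will be determined at a later date based on image grading", makes Visit 8 the main time point, and continues: "The analysis and summaries for any secondary efficacy variables will be the same as that described for the primary efficacy variable". The primary variable is the physician's CGAIS grade, analysed by a repeated-measures mixed model and a paired t-test on change from baseline. The significance criterion is worded for a comparison of groups: "Statistical significance with respect to the treatment group comparison at visit 8 will be declared if the two-sided p-value is < 0.05".

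Section 1.2 lists the comparison of baseline and post-treatment photographs under the primary objectives, whereas section 2.16.5 treats image grading as secondary. Section 3.2 asks only that evaluators be blinded if photographs are a primary objective.

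**The concern.** Each pair can yield three yes/no answers, but the success rule needs one rate and one test. Pooling all reads, taking a majority, requiring unanimity and accepting any correct reviewer are all compatible with the text, and they give different rates. The analysis that section 2.16.5 carries over does not settle the matter: an identification is right or wrong, has no baseline value and so has no change score.

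The study is open label and the treating investigator scores the CGAIS, so the photograph reads are the only assessment described as blinded. If the rule is set after the reads are in, that evidence loses much of its protection. If the reads are pooled as though independent, the error bar is too small, because three reviewers are looking at the same subject.

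**Working it through.** **Inputs.** From the plan: three reviewers; 120 subjects including departures (2.16.2), taken as the upper limit on evaluable pairs; two-sided 0.05; the 80% threshold. Assumed, because the plan gives none of them: one pair per subject, all three reviewers reading it, a 50% chance of a correct guess, per-reviewer accuracy p, and within-subject correlation r between reads (beta-binomial model). Section 2.16.2 gives no effect size or power for the 120, so there is no stated calculation to reproduce.

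**Significance cut-off (exact binomial against 50%).**
- By subject, n = 120: 72 correct (60.0%) gives p = 0.035; 71 gives p = 0.055. The cut-off is 72.
- Pooled reads, n = 360: 200 correct (55.6%) gives p = 0.040; 199 gives p = 0.051. The cut-off is 200.

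**True type I error of the pooled test.** Under guessing, the variance of the pooled count is 360 × 0.25 × (1 + 2r) = 90(1 + 2r). With continuity correction, z = (199.5 − 180)/√(90(1 + 2r)):
- r = 0: 19.5/9.49 = 2.06, error 4.0%
- r = 0.3: 19.5/12.0 = 1.63, error 10.4%
- r = 0.5: 19.5/13.4 = 1.45, error 14.6%
- r = 1.0: 19.5/16.4 = 1.19, error 23.5%

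The exact beta-binomial sum over 120 subjects gives the same figures to one decimal place.

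**Where pooled and majority verdicts differ (expected rates).** The expected pooled rate is p, so it reaches significance at p = 55.6%. The majority rate must reach 60.0%.
- Independent reads: majority = 3p² − 2p³. At p = 0.567 this is 0.964 − 0.365 = 0.600. The verdicts differ for p from 55.6% to 56.7%.
- r = 0.5: majority = p(p + 1)(5 − 2p)/6. At p = 0.593 this is 0.593 × 1.593 × 3.814/6 = 0.600. The verdicts differ for p from 55.6% to 59.3%.

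**The 80% figure taken alone.** With independent reads, majority reaches 80% at p = 0.713 (1.525 − 0.725 = 0.800), whereas pooled needs p = 0.80. At r = 0.5 the band is 78.4% to 80% (0.784 × 1.784 × 3.432/6 = 0.800). Throughout these bands the significance arm is already met: 86/120 (72%) gives p = 2 × 10⁻⁶. Even with perfectly correlated reviewers, 71.3% of 120 subjects gives z = 0.213/√(0.25/120) = 4.7.

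**A rule that the text does not exclude.** If any one correct reviewer counts, reviewers guessing independently score 1 − 0.5³ = 87.5%, and reach 96/120 with probability 0.99. This depends on independence: the rate under guessing falls to 80%, 72.5% and 65% at r = 0.2, 0.4 and 0.6.

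**The case against.** The strongest reply is that the choice seldom matters. The success rule is met by significance or by 80%, and reviewers who see a clear effect will pass under pooling and under majority alike. A reader might infer that the combining rule decides the outcome for any accuracy between 71.3% and 80%. It does not: in that range it decides only whether the 80% figure itself is reached, and the band narrows as reads become correlated. Nor does averaging the three reviewers' rates add a further answer, since with complete reads it equals the pooled rate.

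Two other inferences go too far. The plan does not say that reads will be pooled as independent, so the inflated type I error is the cost of one permitted option and not a property of a stated analysis. The deferral in section 2.16.5 leaves a late choice open; it does not show that one will be made.

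It may also be said that this is a feasibility study, and that a graded image scale could later be defined to suit the carried-over model. Both are fair as context. However, section 2.16.1 sets its own pass/fail rule, and identification is the only photograph task described. The gap and the mismatch with the carried-over analysis stand.

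**Conclusion.** The point holds as a gap in pre-specification. No section sets one result per subject, and the analysis in section 2.16.5 cannot be applied to correct/incorrect identifications. The effect on the overall verdict, comparing pooled with majority, is confined to accuracies near the significance boundary: about 1 percentage point wide with independent reads and about 4 points at correlation 0.5. The larger hazards are a pooled test with a type I error of 10% to 24% at correlations of 0.3 to 1.0, and an any-reader rule that independent guessing would almost always pass.

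These figures rest on the assumed 50% chance level, 120 evaluable pairs and complete triple reading. Fewer evaluable pairs would raise the cut-offs. It is also unsettled which success rule applies. If the photographs are a primary objective, as section 1.2 has it, the secondary rule in section 2.16.1 does not clearly cover them, and the primary criterion there does not mention them.

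**What to change.** Amend sections 2.14 and 2.16.5 before any image is read:
- All three reviewers read each baseline versus Visit 8 pair.
- Each subject has one result: correct if at least two of the three identify the pre-treatment image.
- The rate is tested against 50% with an exact binomial test and given with an exact 95% confidence interval. Subjects are the denominator. This replaces the carried-over mixed model and paired t-test for this variable.
- Each reviewer's own rate and kappa are reported alongside.
- Sections 1.2 and 2.16.5 are reconciled on whether the photographs are primary or secondary, and section 2.16.1 states which success rule applies.

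The cost is a few sentences, with no extra reviewers or subjects. The analysis has at most 120 units instead of 360, so the interval is wider. Majority also reaches 80% at a lower reviewer accuracy than pooling does, which is a reason to fix it in advance and to show the individual rates.

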## 2.2 Protocol Study Design

This is a prospective, open label, multi-center clinical study

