#### Adverse Events Pertaining to the Potenza™ Device:

- Temporary erythema: area of treatment may turn red right after treatment, but this symptom disappears within 48 hours after treatment
- Temporary tingling: slight edema may occur right after treatment, but this symptom disappears within 48 hours after treatment.
- Burning sensation: patients may feel uncomfortable temporarily while receiving treatment.

Other possible adverse effects may include pain/tenderness, pinpoint bleeding, folliculitis, skin burn, hypopigmentation, hyperpigmentation, infection, paresis, scarring, bruising, acne, dryness, eye twitching, eye tearing, petechiae, skin textural irregularity, and allergic reaction which may be transient and resolve over time.

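### The only blinded assessment shows whether two images differ, not whether the treated condition improved, and the image-based secondary variable is still to be chosen

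*Combined protocol and SAP*

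**What the plan says.** The Blinded Evaluation part of section 2.14 states: "Three blinded independent reviewers will perform a photographic evaluation". In it, "they will be asked to identify pre-treatment images when compared to post treatment images". The readers are trained beforehand. No improvement scale, direction of change, image visit, presentation order, rule for combining three answers or success threshold is given.

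The other efficacy ratings are not blinded. Section 2.2 reads: "This is a prospective, open label, multi-center clinical study". The CGAIS "will be used to judge the improvement as seen by the treating Investigator". Satisfaction comes from the subject: "The subject will be asked their level of satisfaction using a 6-point Likert scale". Histology (2.14, Skin Biopsies) is supplied by the investigator, with no blinding stated.

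Section 2.16.1 counts a secondary objective as met if an assessment is statistically significant or reaches an 80% response rate. Section 1.2 lists the blinded photograph evaluation among the assessments, and also puts comparison of baseline and post-treatment photographs among the primary objectives. Section 2.16.5 says: "The secondary efficacy variables will be determined at a later date based on image grading". It makes Visit 8 the primary time point for those variables and sets a two-sided 0.05 level. Section 2.16.3 allows interim reporting, and section 5.0 lets the sponsor request data after each visit.

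**The concern.** Telling before from after is not a measure of benefit. Section 2.15 lists among possible device effects "hypopigmentation, hyperpigmentation, infection, paresis, scarring, bruising", together with skin burn and textural irregularity. Any of these, if still visible when the later photograph is taken, can help a reader place the two images in time. Nothing in 2.14 or 2.16 requires that the difference a reader detects be an improvement.

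What is at stake is the one check that does not depend on the treating investigator or the subject. Section 3.2 relies on blinded evaluators to limit bias in photographic results. A sorting task cannot do that for the CGAIS, because it records neither direction nor size of change. Leaving the image variable open while outcomes can be seen also allows it to be chosen with results in hand.

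**Working it through.** **No plan figure to reproduce.** Section 2.16.2 gives 120 subjects, departures included, without an effect size, rate, standard deviation or power. The calculation below is an illustration only.

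**Inputs.** From the documents: 120 subjects (2.16.2), two-sided 0.05 (2.16.5), significance or at least 80% (2.16.1), three readers (2.14). Assumed: one answer per subject, 50% correct by guessing, no true benefit, and a share *c* of pairs in which something other than benefit reveals the order.

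**Formula.** P(correct) = c + (1 − c)/2 = 0.5 + 0.5c.

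**Significance route.** The exact binomial test against 0.5 first reaches two-sided p < 0.05 at 72/120 = 60% (p = 0.035; 71/120 gives 0.055). With fewer evaluable pairs the bar is 61/100 or 39/60. Probability of reaching it:

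| c | P(correct) | n = 120 | n = 100 | n = 60 |
|---|---|---|---|---|
| 0% | 0.50 | 0.018 | 0.018 | 0.014 |
| 10% | 0.55 | 0.156 | 0.134 | 0.076 |
| 20% | 0.60 | 0.540 | 0.462 | 0.257 |
| 30% | 0.65 | 0.892 | 0.828 | 0.559 |

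**80% route.** Reading the response rate as the share of pairs sorted correctly, 96/120 is needed. The probability is 0.009, 0.122, 0.554 and 0.947 at c = 40%, 50%, 60% and 70%. This route needs far more cues.

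**Cues that mislead.** If a share *d* of the cue-bearing pairs is sorted the wrong way, P(correct) = c(1 − d) + (1 − c)/2 = 0.5 + c(0.5 − d). With c = 20%:
- d = 0.25 gives 0.5 + 0.2 × 0.25 = 0.55, the same as the 10% row.
- d = 0.5 gives 0.50, plain chance.
- d = 1 gives 0.5 − 0.2 × 0.5 = 0.40, below chance.

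The same harms can push the rate up or down, depending on a reader strategy that the plan does not set.

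**Combining three readers.** Under independent guessing:
- At least one of three correct: 1 − 0.5³ = 0.875 of pairs, which meets the 80% bar at n = 120 with probability 0.993.
- Majority correct: 3 × 0.125 + 0.125 = 0.50.
- All three correct: 0.5³ = 0.125.

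The missing rule alone can decide the result.

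**The case against.** Several points on the other side stand.

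- *Scoring is undefined.* A reader might infer that a scar or pigment change is scored as a success. The documents do not say so. A reader who takes the worse-looking image as the earlier one would score it as an error. What the text supports is that it can count either way.
- *Biopsy scars.* Up to 6 of 120 subjects (5%) enter the biopsy portion, and one might infer that their scars appear in graded images. Section 2.10 names both the test spot area and the treatment area as the biopsy site, and 2.7 puts test spots somewhere inconspicuous, such as behind the ear. Those passages need reconciling, and the 5% is at most an upper bound.
- *Hair.* Section 2.6 says: "Shave visible hair from the treatment area". Section 13.0 does not mention hair. But the order of shaving and baseline photography is not stated, a hair difference does not by itself show which image came first, and 13.0 does ask for standardised, comparable photographs. This cue is speculative.
- *Size.* No document gives a cue rate. Section 2.15 says the listed effects may be transient, and Visit 8 falls 30 days after the last treatment. One might read the 60% expected rate at c = 20% as reaching significance. It does so only about 54% of the time with 120 pairs, and 60/100 gives p = 0.057.
- *Consequence.* Overall success in 2.16.1 rests on investigator and subject satisfaction and an acceptable side-effect profile. Adverse events are collected separately, and the CGAIS has a category for worsening. The protocol calls itself a feasibility study.
- *A grade may be intended.* Both 2.14 and 2.16.5 mention grading. Neither defines a photographic scale.

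These points limit the size of the problem. They do not give the blinded task a direction, a scoring rule or a prespecified variable.

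**Conclusion.** The point holds in this form. The only blinded assessment can show that images differ but not that the treated condition improved, and the plan allows it to be called a success without an improvement. It therefore cannot corroborate the unblinded CGAIS. The image-based secondary variable is also left open in an open-label study with possible interim reporting.

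The chances of about 0.16, 0.54 and 0.89 rest on assumed cue shares of 10%, 20% and 30%, guessing at 50%, no benefit, cues that always point the right way, and 120 evaluable pairs. Fewer pairs or misleading cues lower them.

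A reader might go further and infer that the study as a whole could be declared successful on harm. The documents do not support that, because the main success rule also requires satisfaction rates and an acceptable side-effect profile. This should be corrected before images are read, but it does not undermine the main success rule.

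**What to change.** **Section 2.14.** Have the same three readers view each baseline/Visit 8 pair in random left-right order. They state which side looks better for the treated condition, or that there is no difference, and grade the size of the difference on a symmetric scale adapted from the GAIS. The existing wording cannot be used unchanged: grade 1 refers to the optimal result for that subject and grade 3 to an indication for re-treatment, and a reader blind to image order can judge neither. After unblinding, count success only when at least two of three readers rate the post-treatment side better. Keep identification as descriptive.

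**Section 2.16.5.** Before any image is read, name this variable, Visit 8, the majority rule and one success threshold: either the 80% already in 2.16.1 or a two-sided test of better against worse. Reconcile its secondary status with the primary objective in 1.2.

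**Section 13.0.** Ask for the same hair state in both photographs, and keep any biopsied site out of the graded field.

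**Cost.** Wording in three sections and one more answer per pair, from readers and a training session already planned. The blinded success rate will probably be lower than the identification rate.
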